**Safety assessment parameters**

|                                  |  |
|----------------------------------|--|
|                                  | 
Safety evaluation is based on the following parameters (between V1 and V3) compared between therapy and placebo groups.
 
Frequency of adverse events (AEs) and/or serious adverse events (SAEs) in the treatment groups, including:
 
 
- Overall AE rate as compared to placebo;
 
- Frequency of AEs according to the results of physical examinations during each visit compared with placebo;
 
- AE incidence according to the results of the vital signs assessment (HR, BP, BT, RR) at each visit in comparison with placebo;
 
- AE incidence according to the ECG results on Day 15 (<math>\pm 2</math>) in comparison with placebo;
 
- Frequency of AEs incidence according to the results of laboratory examinations on Days 7(<math>\pm 2</math>) and 15(<math>\pm 2</math>) compared with placebo;
 
- Frequency of AEs according to the patients' records in the diary
 
 
Diary records will be reviewed by the Investigator and for those records presumed to meet criteria of an AE, the patient will be questioned. If the investigator judges that the AE criteria have been met, all information relevant for an AE (including an evaluation of causality to the investigational product) will be documented.
 
The AEs will be described according to the scheme given below:
 
 
- AE description;
 
- AE severity;
 
- AE duration;
 
- Causal relationship with the investigational product;
 
- Outcome.
 
 
All AEs will be coded according to MedDRA terms.
 |
| 
Inclusion Criteria
 | 
Patients will be considered eligible if they meet the following inclusion criteria:
   |

|  |  |
|--|--|
|  | 
1. An Informed Consent Form for study participation voluntarily signed by a patient;
 
2. Male and female subjects, 18 to 65 years of age inclusive;
 
3. Antibacterial treatment for active ARD started/to be started on the first day of the study (7-day course of oral beta-lactam antibiotic). Only one AB should be used per subject, in an outpatient setting. Diagnosis of acute respiratory infections and the prescription of antibiotic therapy should be completed before signing of the Informed Consent Form.
 
4. Female patients are eligible for the study if they are:
 
 
• Unable to become pregnant (i.e. postmenopausal women or those after surgical sterilization). Surgically sterile women are defined as patients with documented hysterectomy, and/or bilateral oophorectomy, and/or tubal ligation. Postmenopausal women are defined as women with amenorrhea for more than 1 year with the relevant clinical profile (e.g., age > 45 years, and absence of hormone replacement therapy). However, in controversial cases, it is recommended to confirm menopause by drawing a blood sample which would show an FSH level of > 40 IU/mL and estradiol level of < 40 pg/mL (< 140 pmol/L).
 
• OR
 
 
Capable of childbirth, but with negative pregnancy test at the screening visit, and the patient agrees to continuously and properly use one of the following suitable methods of contraception (i.e., in accordance with the approved Package Insert for the medicinal product and physician instructions) during the participation period:
 
 
a. Complete abstinence;
 
b. Oral contraceptives (combination drugs containing progestogen, or progestogen alone);
 
c. Injectable progestogen;
 
d. Levonorgestrel implants;
 
e. Estrogen-containing vaginal ring;
 
f. Transdermal contraceptive patches;
 
 |
|--|--|

|                                      |   |
|--------------------------------------|---|
|                                      | 
 
g. Intrauterine device or intrauterine system;
 
h. A male partner has been sterile (vasectomy with documented azoospermia) prior to inclusion of a woman, provided that he is the only partner of the female patient. For the purpose of this definition, "documented" is related to the result of a subject's medical examination performed by Investigator/responsible person or a subject's past medical history review for assessment of eligibility for enrollment, obtained during the interview with a subject or from his/her medical records;
 
i. Double barrier method: a condom or an occlusive cap (diaphragm or cervical/vault caps) with a spermicide (foam/gel/film/cream/suppository);
 
 
 
5. Male participants are obliged to use appropriate contraception during the entire study period starting from signing of the Informed Consent Form and until the study end, and for 30 days after study completion;
 
6. The ability to understand the information about the clinical study, readiness to comply with the study protocol requirements, ability to take IP and evaluate symptoms on his (or her) own using diary/questionnaires as per protocol;
 
7. Ability to maintain the habitual lifestyle throughout the study, including diet.
 
8. Willing not to consume any products containing probiotics during participation in the clinical trial.
 
9. Willing not to take part in any other study during the present study.
 
 |
| 
Non-inclusion Criteria
 | 
Patients will not be eligible for study enrollment if they have one or more of the following criteria:
 
 
1. Any treatment (including medications, medical devices and food supplements) that can influence the stool consistency according to the Investigator's opinion should not be used within 14 days prior to Visit 1.
 
2. Use of anti-rejection medication after stem cell or solid organ transplant;
 
   |

|  |  |
|--|--|
|  | 

3. Use of glucocorticosteroids within the last 8 weeks prior to Visit 1;

4. Use of proton pump inhibitors within 3 months prior to Visit 1;

5. Chemotherapy or radiation;

6. History of recurrent diarrhea;

7. Diarrhea or watery stool in the last 2 days prior to Visit 1;

8. Severe ARD expected to require additional antibiotics or to require antibiotics therapy more than 7 days;

9. Use of antimicrobials in the last 3 months prior to the study start;

10. Use of yeast/probiotic/fermented products within the last 2 weeks prior to V1;

11. Known allergy/sensitivity to the IMP;

12. Immunocompromised patients;

13. Known digestion/absorption disorders of the gastrointestinal tract (e.g. inflammatory bowel disease, coeliac disease, pancreatitis, motility disorders etc.) and/or gastrointestinal surgery (with the exception of appendectomy more than 3 months before Visit 1);

14. Known irritable bowel syndrome;

15. Known small intestinal bacterial overgrowth;

16. Pyrexia > 38 °C;

17. Pregnant and/or breastfeeding women.

18. Participation in other clinical trials of medicinal products or medical devices at the screening Visit or for 30 days before the screening Visit.

19. Surgical intervention for 30 days before the screening visit or planned surgical treatment during the trial (before a follow-up visit is completed), including diagnostic procedures or hospital stay.

20. Known or suspected alcohol and/or drug addiction;

21. A suspected low compliance or incapability of the patient to perform the procedures and comply with restrictions according to the trial protocol (e.g., due to mental disorders);

22. Potential for translocation of probiotic across bowel wall (Presence of an active bowel leak, acute abdomen, active

 |
|--|--|

|                                  |  |
|----------------------------------|--|
|                                  | 
intestinal disease including colitis, or significant bowel dysfunction; presence of neutropenia or anticipation of neutropenia after chemotherapy; radiation therapy);
 
23. Any disorders of cardiovascular, renal, hepatic, gastrointestinal, endocrine, or nervous disorders, and other conditions/diseases which, in the Investigator's opinion, may render study participation unsafe for a patient or may affect a test result.
 
24. Positive result of express-test for detection of IgM antibodies for COVID-19.
   |
| 
Exclusion Criteria
 | 
Subject participation will be stopped in case any of the following reasons occur:
 
 
1. Disease progression (including pyrexia above 38 °C for 3 days or longer);
 
2. Positive culture or PCR results for Shigella and Salmonella spp, typhoid and paratyphoid species, pathogenic E. coli, and other pathogen species (including C. difficile), if supplementary antibacterial treatment is required during the study;
 
3. Need to change tactics of antibiotic therapy (extension course of antibiotic therapy or change of antibiotic group);
 
4. The Ethics Committee, regulatory authorities, or Sponsor terminate the trial or participation of the specific trial site for any reason;
 
5. The Investigator's decision to withdraw the patient from the trial in the interests of the patient;
 
6. Withdrawal of the informed consent (unwillingness of the patient to continue his/her participation in the study);
 
7. Individual intolerance of Investigational products (according to Investigator's judgment);
 
8. Clinically significant adverse event or serious adverse event;
 
9. Patient's non-compliance;
 
10. Error enrollment (e.g., the patient was included with violation of the inclusion/non-inclusion criteria);
 
11. The patient complies with the non-inclusion criteria during the study;
 
 |

|   |  |
|---|--|
|   | 
12. The patient receives or requires an additional therapy which might influence the study results or patient's safety (see Prohibited concomitant therapy section);
 
13. Other conditions or events which, in the Investigator's opinion, require the patient's exclusion from the study.
  |
| 
Prohibited Concomitant Treatments
 | 
 
1. Systemic glucocorticosteroids within 8 weeks prior to and during the study;
 
2. Use of any antibacterials in the last 3 months prior to the study or of any antibacterials (except the AB per inclusion criterion 3) during the study;
 
3. Use of any proton pump inhibitor within 3 months prior to the study;
 
4. Other probiotics (bacteria or yeast, medications, food supplements, fermented products) and Broncho-munal® within 2 weeks prior to and during the study;
 
5. Any treatment (including medications, medical devices and food supplements) that can influence the stool consistency according to the Investigator's opinion within 14 days prior to and during the study (other than the drugs specified in items 3 and 4 of the Allowed Concomitant Treatments).
 
 
See the list of prohibited drugs in Appendix No. 1.
 |
| 
Allowed Concomitant Treatments
    | 
 
1. Oral beta-lactam antibiotic (for instance, amoxicillin, amoxicillin + clavulanic acid, cefixime, etc.) (see Background Antibacterial Therapy) as per inclusion criterion 3, in the same dosage regimen as at study start.
 
2. Continuation of the drug administration started prior to the inclusion into the study for treatment of concomitant diseases not covered by any of the exclusion criteria. Continuation of oral contraceptive administration by female participants during the study.
 
3. Standard symptomatic treatment agents used to treat acute respiratory infections in case of medical need, including anilides, triazole derivatives, with the exception of drugs that can have a laxative effect (for example, throat lozenges with sugar substitutes)/
 
   |

|                                    |  |
|------------------------------------|--|
|                                    | 
4. Agents for relieving symptoms of acute diarrhea, in case of medical need, including electrolyte solutions, with the exception of sorbents.
 
Prescribing therapy for acute diarrhea and acute respiratory infections is possible only by the decision of the investigator.
  |
| 
Statistical Analysis
 | 
The aim of the statistical analysis will be to prove the efficacy and safety of LRG-002 (Lactobacillus rhamnosus GG not less than <math>2 \times 10^{10}</math> CFU) to be superior to placebo in antibiotic-treated patients with acute respiratory diseases, as an adjunct treatment for prophylaxis of antibiotic-associated diarrhea (AAD).
 
The analysis will be performed for comparison of:
 
 
- LRG-002 and matching placebo.
 
 
The primary efficacy endpoint will be analyzed with a logistic regression model with fixed factors for treatment group and age group.
 
The primary efficacy endpoint will be considered achieved if the odds ratio for the occurrence of AAD between placebo and LRG-002 is significantly higher than 1 (i.e. the occurrence of AAD is lower in the LRG-002 group).
 
The secondary parameters will be compared with the following method:
 
 
- continuous variables will be compared by Mann—Whitney-Wilcoxon test.
 
 
Binary and ordinal variables will be compared by chi- square test or Fisher's exact test (depending on the number of expected observations per cell: <math><5</math> or <math>\geq 5</math>).
 
The analysis of study subjects with AE (SAE) will be performed with chi-square test or Fisher's exact test.
 
Poisson regression will be used for analysis of AE (SAE) frequency. The significance level is assumed as <math>p < \alpha</math>, with <math>\alpha = 0.05</math>.
 
Sample size calculation
 
Primary endpoint is the frequency of occurrence of AAD from the
 |

first to the last day of LRG-002 administration compared with placebo in antibiotic-treated patients with ARDs.

A test based on odd ratio was used to calculate sample size.

The following parameters were obtained from Figure 2 in a meta-analysis [1] using only data for AAD:

Using only data for AAD studies in adults from the cited publication, the rate for the control group is 0.24 and for the treatment group 0.14.

Using only data for LGG studies in adults and children, the rate for the control group is 0.26 and for the treatment group 0.15.

In meta-analysis [14] figures from Table 1 demonstrate a rate of 0.196 for a treatment group and 0.29 for a placebo group (only trials for adults with LGG were taken into consideration).

In meta-analysis [15] figures from Table 2 demonstrate a rate of 0.188 for a treatment group and 0.269 for a placebo group (only trials for adults with LGG were taken into consideration).

Consideration of AAD studies for LGG from [16], concerning infections at adults (including *H. pylori*), results in 0.14 for a probiotic group and 0.22 for a control group.

Combining all the strains, we obtain an incidence of 0.26 for placebo and an incidence of 0.15 for treatment.

The following indicators were used for calculations:

1. Difference of absolute risks of AAD in placebo group and in treatment group is expected to be positive.
2. Incidence of AAD 0.26 is assumed for a placebo and 0.15 for the treatment.
3. Probability of type I error: 0.05;
4. Power of the study is 80%, which corresponds to the type II error: 0.20.
5. Statistical hypothesis is the evidence of superior efficacy:

H0: OR=1

H1: OR≠1,

where OR is the odds ratio between both groups.

The ratio between the study and control group sizes is 1:1.

The number of patients in each group could be calculated using the following formula [2]:

$$n_T = n_T = \left( \frac{Z_{1-\alpha/2} + Z_\beta}{p_T - p_R} \right)^2 [p_T(1-p_T) + p_R(1-p_R)] = 208$$

Thus, the minimum number of patients required for statistical analysis is 416 (208 patients in each group). Taking into account a 20% withdrawal rate, one needs to randomize 520 subjects (260 patients in each group).

1. Efficacy of probiotics in prevention of acute diarrhea: a meta-analysis of masked, randomized, placebo-controlled trials. Sazawal S, Hiremath G, Dhingra U, Malik P, Deb S, Black RE. Lancet Infect Dis. 2006 Jun; 6(6):374-82. Review. PMID:16728323. DOI:10.1016/S1473-3099(06)70495-9
3. Prophylaxis against ampicillin-associated diarrhea with a lactobacillus preparation. Gotz V., Romankiewicz J. A., Moss J. and Murray H. W. Am J Hosp Pharm. 1979 Jun; 36:754-757. PMID: 12052801. DOI: 10.1136/bmj.324.7350.1361.
4. Double-blind report on the efficacy of lactic acid-producing Enterococcus SF68 in the prevention of antibiotic-associated diarrhoea and in the treatment of acute diarrhoea. Wunderlich P.F., Braun L., Fumagalli I., D'Apuzzo V., Heim F., Karly M., Lodi R., Politta G., Vonbank F., Zeltner L. J Int Med Res. 1989 Jul-Aug; 17(4):333-8. PMID: 2676650. DOI: 10.1177/030006058901700405

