**1. Synopsis**

|  |   |
|--|---|
| Study Title                             | Multi-center, double-blind, randomized, placebo-controlled, parallel-group study of the efficacy and safety of LRG-002 hard capsules (Lek d.d., Slovenia) in the prophylaxis of antibiotic-associated diarrhea in adults.   |
| Study Code                              | CT_002_LRG_CAP  |
| Sponsor                                 | Sandoz CJSC   |
| Investigational Medicinal Product       | LRG-002 = hard capsules with Lactobacillus rhamnosus GG not less than $1 \times 10^{10}$ CFU per capsule (Lek d.d., Slovenia)   |
| Reference product                       | Matching placebo, capsules  |
| Background Antibacterial Therapy        | Oral beta-lactam antibiotics, e.g. amoxicillin, Augmentin (amoxicillin clavulanate), cefixime, etc. (7-day course). The start of antibiotic therapy coincides with the first day of the study.

Diagnosis of the underlying disease and the prescription of antibiotic therapy are not part of the study. |
| Phase of the Clinical Study             | III   |
| Study Population                        | It is planned to include (randomize) 520 patients (260 patients in each treatment group) taking into account a patient withdrawal rate of 20% or less. The minimal number of patients needed for statistical analysis is 416 patients with 208 patients of the per-protocol population in each treatment group. |
| Planned Study Duration                  | Maximum 17 days:
Day 1: Screening/randomization/study treatment initiation
Day 7 ± 2: Intermediate Follow-up Visit
Day 15 ± 2: Treatment Completion / Study Termination Visit (after completion of LRG-002/Placebo regimen)

The overall enrollment period is about 8 months.                    |
| Planned Number of Investigational Sites | Up to 40 sites in the RF  |

|                                 |   |
|---------------------------------|---|
| 
Study Goal
        | 
To demonstrate the efficacy and safety of the investigational medicinal product LRG-002 as compared with placebo, as an adjunct treatment for prophylaxis of antibiotic-associated diarrhea (AAD) in patients with acute respiratory diseases (ARDs) receiving a standard antimicrobial regimen.
   |

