## **5.4 Measures aimed at minimizing/eliminating subjectivity**

### **5.4.1 Randomization**

The study will be double-blinded, randomized.

Patients will be included by applying stratified randomization in two strata:

- age <50 years
- age ≥ 50 years

Each treatment group will be balanced at a ratio of 1: 1 within each stratum.

Stratified randomization is a two-stage procedure in which patients who enter a clinical trial are first grouped into strata. Within each stratum, patients are then assigned to a treatment according to separate randomization schedules. Randomization module of EDC system assigns patient unique randomization code based on group of treatment and stratum. Randomization schedules will be hidden from medical personnel and all other persons involved in the study (monitors, data management, biometry, sponsor etc.), except the specialists responsible for labeling of the investigational medicinal products, and the emergency unblinding.

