7.1. Primary endpoint analysis

Assessment of the incidence of AAD from Day 1 to the last day of the course of LRG-002 use vs. placebo in ARD patients receiving standard antimicrobial therapy. The primary efficacy criterion will be considered met if the odds ratio for AAD between the two groups is statistically significantly greater than 1 (i.e., the incidence of AAD in the LRG-002 group is lower than in the placebo group).

STATISTICAL ANALYSIS PLAN

The primary efficacy endpoint will be analyzed using a fixed-factor logistic regression model for the treatment group and age group. The treatment effect will be displayed using the adjusted odds ratio and the corresponding two-sided 95% confidence interval.

PCT will be calculated using the following set of functions of the R language:

- `glm` – building a logistic regression model;
- `summary` – displays the regression coefficients with an indication of the statistical significance;
- `confint` – displays confidence intervals for regression coefficients.

An example of a planned way of using these functions is shown in Figure 2. In the figure, the *Outcome* variable encodes the outcome (AAD – yes/no), *Treatment* encodes belonging to a particular study group, the *Age* variable encodes the age category (over or under 50 years old). The *p*-value is highlighted in red, the two-sided confidence interval is highlighted in blue, according to which the decision on reaching the PCT will be made.

```
> model_out <- glm(Outcome ~ Treatment + Age, data = df, family = "binomial")
> summary (model_out)
Call:
glm(formula = Outcome ~ Treatment + Age, family = "binomial", data = df)
Deviance Residuals:
    Min       1Q   Median       3Q      Max
-0.3327 -0.3327 -0.1635 -0.1635  2.9402

Coefficients:
            Estimate Std. Error z value Pr(>|z|)
(Intercept)  -4.3090    0.5949  -7.243 4.4e-13***
Treatment2    1.4427    0.6520   2.213 0.0269*
Ageage >=50  -0.5368    0.6558  -0.819 0.4130
```

```
Signif. codes: 0 '****' 0.001 '**' 0.01 '*' 0.05 '.' 0.1 ' ' 1

(Dispersion parameter for binomial family taken to be 1)

Null deviance: 135.35 on 509 degrees of freedom Residual deviance: 128.52 on
507 degrees of freedom
AIC: 134.52

Number of Fisher Scoring iterations: 7

> confint(model_out)
Waiting for profiling to be done...
      2.5%      97.5%
(Intercept) -5.7259968 -3.3150721
Treatment2  0.2808742  2.9311963
Age >=50    -2.0306660  0.6338301
```

Figure 2. Running functions for calculating PCT

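### The primary model omits which beta-lactam was prescribed, a variable fixed before randomisation; the likely cost is a small loss of precision, not bias

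*Protocol*

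**What the plan says.** The Protocol Synopsis (Statistical Analysis) states: "The primary efficacy endpoint will be analyzed with a logistic regression model with fixed factors for treatment group and age group". Protocol 10.1.2 repeats this. SAP 7.1 says "The primary efficacy endpoint will be analyzed using a fixed-factor logistic regression model for the treatment group and age group", shows the call "glm(formula = Outcome ~ Treatment + Age", and bases the decision on the p-value and confidence interval of the treatment coefficient from that model.

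On allocation, Protocol 5.4.1 says "Patients will be included by applying stratified randomization in two strata", namely age under 50 and age 50 or over. SAP 4.1 agrees.

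On the antibiotic, the Synopsis allows "Oral beta-lactam antibiotics, e.g. amoxicillin, Augmentin (amoxicillin clavulanate), cefixime, etc. (7-day course". Inclusion criterion 3 adds "Only one AB should be used per subject, in an outpatient setting", and requires that "the prescription of antibiotic therapy should be completed before signing of the Informed Consent Form". Concomitant treatment is recorded at Visit 1, and Protocol 7.3 lists the beta-lactam among the allowed concomitant treatments. No separate field for the agent is named. The diary asks only whether the antibiotic was taken as prescribed, not which one it was.

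Two provisions come close to the issue:

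- Protocol 10.1.1 and SAP section 5 compare pre-treatment data between arms and add a covariate-adjusted analysis if a difference is statistically significant.
- Protocol 10.1.2 promises a look at centre effects and leaves room for further sensitivity analyses. The SAP names none by antibiotic, and SAP section 9 foresees no exploratory analysis.

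**The concern.** The antibiotic is the exposure that defines the endpoint, and it differs between patients. Because it is settled before randomisation, it is a legitimate baseline covariate that needs no new procedure. Randomisation takes no account of it, so the arms will differ in antibiotic mix by chance. If some permitted agents carry a higher AAD risk than others, part of the observed difference in a given trial reflects that mix, and the primary analysis does nothing to remove it. What is at stake is precision, and how readily a reader accepts the primary result if the mix turns out uneven.

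**Working it through.** **Inputs from the documents.** AAD 0.26 on placebo and 0.15 on LRG-002, two-sided alpha 0.05, power 80%, 1:1 allocation, 208 evaluable and 260 randomised per group (Protocol 10.3, 10.4; SAP 2.3).

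**Assumptions, because the documents give no AAD rate by agent and no prescribing mix.** Two types of agent, split 50:50 (30:70 as a check); odds ratio for AAD between types from 1 to 4; marginal rates held at 0.26 and 0.15. Age is left out of the calculation.

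**1. The plan's own figure.** (1.960 + 0.842)² × [0.15×0.85 + 0.26×0.74] / 0.11² = 207.5, so 208. Then 208 / 0.80 = 260. Both reproduce.

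**2. Power without the agent.** Treatment odds ratio = (0.26/0.74) / (0.15/0.85) = 1.991, log 0.689. Standard error at 208 per group = √[(1/(0.15×0.85) + 1/(0.26×0.74)) / 208] = 0.250. Power = Φ(0.689/0.250 − 1.960) = 78.5%. At 260 per group it is 86.8%.

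**3. Power with the agent in the model.** Within each agent group, let w = N·p(1−p) in each arm. The information on treatment is the sum over groups of w_P·w_T / (w_P + w_T). At an agent odds ratio of 2 and 104 patients per cell:

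- Placebo rates are 0.194 and 0.326, and the treatment odds ratio within agent is 2.017. The LRG-002 rates are then about 0.107 and 0.193.
- Information is about 6.16 + 9.49 = 15.64, so the standard error is 0.253.
- Power = Φ(0.702/0.253 − 1.960) = 79.25%.

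| Agent odds ratio | Placebo AAD by agent | Treatment OR given agent | Power, 208 per group: without → with | Power, 260 per group: without → with |
|---|---|---|---|---|
| 1 | 26.0% / 26.0% | 1.991 | 78.53 → 78.53 | 86.76 → 86.76 |
| 1.5 | 22.1% / 29.9% | 2.000 | 78.53 → 78.78 | 86.76 → 86.96 |
| 2 | 19.4% / 32.6% | 2.017 | 78.53 → 79.25 | 86.76 → 87.34 |
| 3 | 15.9% / 36.1% | 2.054 | 78.53 → 80.24 | 86.76 → 88.14 |
| 4 | 13.5% / 38.5% | 2.089 | 78.53 → 81.12 | 86.76 → 88.84 |

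With a 30:70 mix and 208 per group, adjusted power at odds ratios 1.5, 2, 3 and 4 is 78.76, 79.23, 80.35 and 81.46%. Simulation of 60,000 trials per scenario (50:50, 208 per group) gives changes of −0.2, +0.1, +0.5, +1.4 and +2.2 points at odds ratios 1, 1.5, 2, 3 and 4, in line with the table.

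**4. Size of chance imbalance.** The SD of the between-arm difference in agent share is √(2 × 0.25 / 208) = 4.9 points. At an odds ratio of 2 this moves the risk difference with an SD of about 0.6 points (0.049 × 0.132); at 4, about 1.2 points (0.049 × 0.25). The sampling standard error of the risk difference is √[(0.1275 + 0.1924) / 208] = 3.9 points.

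**5. Type I error.** Simulated with 26% in both arms, the unadjusted test rejects in 4.8 to 5.1% of trials in every scenario.

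**6. Reach of the baseline rule.** Significance needs a difference of about 1.96 × 4.9 = 9.6 points, which occurs in about 5 to 6% of trials. A difference of 5 points or more occurs in about 30%. So in roughly a quarter of trials the agent share differs by 5 points or more and no adjusted analysis is triggered.

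**The case against.** The strongest case against acting is that exposure is already narrow (one class, one oral agent per patient, a 7-day course), that the primary model adjusts for exactly the randomisation stratum, that a prespecified rule answers significant imbalance, and that nothing in the documents shows AAD risk to differ between permitted agents. The gain at a moderate odds ratio is then under one point.

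Most of this stands, and it limits the point to a minor one. It does not remove it. The baseline rule adds an analysis beside the primary one, so the success decision stays unadjusted. It also responds to the size of an imbalance rather than to whether the variable predicts AAD. Nor do the documents give AAD rates for the two age groups, yet age is in the model.

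A reader might go further in two ways that the documents do not support.

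- **That the comparison is biased or false positives are inflated.** Averaged over randomisations, type I error stays at 5%. Only in trials picked out for a significant agent imbalance does the unadjusted rate rise, to about 6% at an odds ratio of 2, 7% at 3 and 8 to 10% at 4. That describes a selected 5 to 6% of trials, not the design.
- **That the protocol itself shows the agent matters.** Protocol 3.2.2.11 reports in-vitro susceptibility of LGG, which bears on whether the probiotic survives, not on AAD risk by agent. The H. pylori subgroup in 3.3.3.2 is a treatment effect, and the eradication trials of LGG described in 3.3.3.3 used rabeprazole, clarithromycin and tinidazole, with no beta-lactam. Both would concern effect modification, which a main-effect term does not address.

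**Conclusion.** The point holds as a minor, nearly free improvement. The primary model leaves out a baseline variable closely tied to the endpoint. If agents differ in AAD risk, power falls short by about 0 to 1 point up to an odds ratio of 2 and by about 1.5 to 3 points at 3 to 4, and chance imbalance in agent stays in the primary estimate. If they do not differ, nothing is lost and adjusting costs essentially nothing.

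These sizes rest on assumed agent effects, an assumed mix, and a grouping that captures the real contrast. A poorer grouping would gain less.

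**What to change.** In the Synopsis, Protocol 10.1.2 and SAP 7.1, add the antibiotic prescribed at Visit 1 as a prespecified fixed factor: `glm(Outcome ~ Treatment + Age + Antibiotic)`. Use a small number of groups, set from blinded prescribing data and fixed before unblinding. The documents give no basis for naming a particular split now. Confirm that the agent has its own eCRF field rather than sitting only among general concomitant medication. Keep the two-factor model as a sensitivity analysis.

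The cost is a line of wording in each place and one factor in the model. At the design rates about 208 × (0.26 + 0.15) = 85 events are expected, enough to carry a few extra coefficients. No patients or visits are added. The odds ratio becomes conditional on antibiotic as well as age, moving from about 1.99 to 2.02 at an agent odds ratio of 2, so the SAP should state which odds ratio is the target.
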